Duration of administration	Patients are enrolled in the study from time of consent prior to surgery to the end of six months of the follow up period.
Reference methods	N/A
Statistical Considerations	Descriptive statistics will be present (mean and standard deviation) with 95% confidence intervals. We are planning to collect ICG data before and after the debridement. Pearson correlation between ICG parameters (pre-debridement, or/and post-debridement, or/and changes between pre- and post-debridement) and index infection/recurrent will be calculated for each of three patient cohorts. We will also include the corresponding coefficient of determination indicating how much variation in index infection/recurrent can be explained in ICG parameters. Finally, we will evaluate the significance of the correlation coefficient using two sided t-test. P-value less than 0.05 will indicate that the correlation is significant. Then, we will form receiver operating characteristic (ROC) curves to illustrate graphically the performance and to obtain the threshold for differentiating the recurrent infection from non-infection group, of each chosen model. Area under the ROC curve will be used to determine the optimal property for differentiating the recurrent infection patients from the non-infection patients.

1 Introduction

This document is a clinical research protocol and describes a human research study. This study will be conducted according to US and international standards of Good Clinical Practice (FDA Title 21 part 312 and International Conference on Harmonization guidelines), applicable government regulations and Institutional research policies and procedures. All personnel involved in the conduct of this study have completed human subject protection training and primary oncologic surgeons performing study procedures will be trained on this protocol

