1.5.2 Potential Benefits

Patients enrolling in this study will not benefit directly because no diagnostic or therapeutic decisions will occur based on the study, and thus, administration of the study is not intended to alter the surgical procedure. However, future patients may benefit from the knowledge gained from the study since this study may provide an objective, intraoperative, and real-time methodology to assess bone perfusion and thoroughness of debridement. This method may save the patients from unnecessarily high risk for index infection or nonunion—in the setting of open fracture—or recurrent infection in the setting of established infection, due to the substantial practice variation.

2 Study Objectives

The primary study objective is to establish the range and variation associated with bone/soft tissue perfusion in fracture patients, using ICG fluorescence imaging and examine the relationship between perfusion and complications such as SSI, persistent SSI, and fracture nonunion.

The secondary study objective is to develop intraoperative hardware and software tools that will be used to guide debridement to optimize the quantity of bone/tissue resected to minimize complications.

3 Study Design

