7.1 Sample Size Determination

The participating Statisticians on the study are members of the Norris Cotton Cancer Center and/or Department of Orthopaedics at Dartmouth-Hitchcock Medical Center. Sample size determination is based on the primary objective of the study as a pilot assessment of ICG fluorescence intensity of bone perfusion.

For patient cohort 1, we anticipate that approximately 10% of patients with open fracture will have an SSI within 12 months of their fracture^{1, 2, 32}. A total sample size of 160 patients will result in an estimated 16 patients with an SSI and 144 patients without an SSI. We will have 86% statistical power to detect a mean maximum fluorescence intensity (I_{max}) difference of 24 (a.u.) between the SSI group and the non-SSI group with an estimated standard deviation of 30 (a.u.) and 15 (a.u.), respectively. All parameters were obtained from our previous porcine study. To be conservative, we increased the standard deviation by 50% for this power calculation. The type I error is set to be 5%. If we assume a drop-out rate of 10%, then a total of 176 patients will be enrolled.

For patient cohort 2, we anticipate approximately 30% of patients with an SSI will go on to develop a persistent SSI/treatment failure within 12 months of diagnosis of their SSI¹². Based on this estimate, a sample size of 22 patients with SSIs and 52 patients without, will have 93% statistical power to detect a mean I_{max} difference of 24 (a. u.) between the persistent SSI/treatment failure group and the non-persistent SSI/non-treatment failure group with I_{max} estimated standard deviation of 30 (a. u.) and 15(a. u.). All parameters are obtained from our previous porcine study, which are consistent with a pilot study conducted at STC in human participants using ICG fluorescence for a different indication. To be conservative, we increased the standard deviation by 50% for this study. The type I error is set to be 5%. If we assume the dropout rate is 10%, then a total of 82 patients will be recruited.

For patient cohort 2-1, the strength of the relationship between DCE-MR and DCE-FI measurements will

be assessed by determining the zero-order correlation and resulting R2 metric. A sample of 21 was estimated utilizing formula presented by Bonett & Wright ³⁶ with a Type I error rate of 0.05 and Type II error

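### The ICG threshold and the choice of ICG variable come from the same patients used to show performance, with no internal validation, so sensitivity at an optimised cut-off and the selected AUC would on average be optimistic

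*Combined protocol and SAP*

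**What the plan says.** The Study Summary, under Statistical Considerations, says that ROC curves will be formed to show performance and "to obtain the threshold for differentiating the recurrent infection from non-infection group, of each chosen model". The area under the curve then decides which ICG property separates the groups best. No criterion for placing the cut-off is given.

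Section 7.2 states the primary hypothesis in cohorts 1 and 2 for the post-debridement maximum intensity (I_max-post). In both cohorts, however, the variable carried into the t-test is the kinetic-curve variable with the highest AUC in that cohort. The number of candidates is not stated. The Study Summary mentions pre-debridement values, post-debridement values and their change, so each parameter can appear in at least three forms.

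The expected event counts are in section 7.1. For cohort 1, "A total sample size of 160 patients will result in an estimated 16 patients with an SSI and 144 patients without an SSI". For cohort 2, "a sample size of 22 patients with SSIs and 52 patients without, will have 93% statistical power".

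Section 2 gives as the secondary objective to "develop intraoperative hardware and software tools that will be used to guide debridement to optimize the quantity of bone/tissue resected". Section 1.5.2 says that no clinical decision in this study will rest on the imaging.

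Neither the Study Summary nor section 7.2 mentions a hold-out set, cross-validation, bootstrap, external validation, or a confidence interval for the threshold or its performance.

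**The concern.** A cut-off chosen because it separates the observed events well is fitted partly to the chance positions of a few values. Sensitivity read off at that point in the same data tends to be too high, even for a single pre-named marker that truly works. Choosing the variable by its AUC and then reporting that AUC adds a second source of optimism.

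This is the only decision threshold the plan derives, and section 1.1 and section 2 both look ahead to guiding debridement. A published cut-off with flattering sensitivity would be a poor starting point for that later work.

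**Working it through.** **Inputs (section 7.1).** Mean I_max difference 24 a.u.; "estimated standard deviation of 30 (a.u.) and 15 (a.u.), respectively" (event and non-event group); 16 vs 144 in cohort 1 and 22 vs 52 in cohort 2; type I error 5%. The 50% inflation of the standard deviations is read as already contained in 30 and 15.

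**Plan's own figures first.** Unequal-variance t-test, two-sided, power from the noncentral t:

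- Cohort 1: SE = √(30²/16 + 15²/144) = √57.81 = 7.60; noncentrality 24/7.60 = 3.16; Satterthwaite df 15.8; power 84.1% (stated 86%).
- Cohort 2: SE = √(30²/22 + 15²/52) = √45.24 = 6.73; noncentrality 24/6.73 = 3.57; df 25.6; power 92.9% (stated 93%).

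The inputs are therefore read as the plan intends, to within 2 points. They imply a true AUC of Φ(24/√(30² + 15²)) = Φ(0.716) = 0.763.

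**Simulation.** Events are drawn from N(−24, 30) and non-events from N(0, 15), one variable, low values counted as positive. In each simulated trial a cut-off c is chosen on the sample ROC curve. Apparent sensitivity is the share of sampled events at or below c; true sensitivity is Φ((c + 24)/30). True specificity is 1 − Φ(c/15). The plan names no rule, so several were tried (10,000 to 20,000 trials each). The ranges reflect placing c at an observed value or at a midpoint between values.

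| Mean overstatement, percentage points | Cohort 2 (22 vs 52) | Cohort 1 (16 vs 144) |
|---|---|---|
| Sensitivity, maximum Youden index | 5.7 to 7.3 | 8.4 to 9.4 |
| Sensitivity, closest to the (0,1) corner | 4.9 to 5.8 | 7.0 to 7.5 |
| Sensitivity, specificity fixed at 80% or 90% | 0 to 1.5 | 0 to 0.8 |
| Specificity, maximum Youden index | 2.0 to 3.5 | 0.6 to 1.3 |

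With a Youden cut-off at an observed value, apparent against true sensitivity is 64.6% against 57.3% in cohort 2 (7.3 points) and 65.6% against 56.2% in cohort 1 (9.4 points; rounding to 66% and 56% first makes it look like 10). These are averages: sensitivity is overstated in about 75% of simulated trials with 22 events and 79% with 16.

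**Sensitivity to the standard deviations.** For cohort 2 under Youden, SDs of 20 and 10 give 5.7 points, and SDs of 45 and 22.5 give 6.8. The result does not hinge on how the 50% inflation is read.

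**AUC.** For one pre-named variable the mean empirical AUC was 0.762 to 0.765 against a true 0.763, so there is no bias. Reporting the best of 3 to 6 equally good candidates, with correlation 0.5 to 0.8 (both assumed), inflates AUC by 0.032 to 0.067 in cohort 2 and by 0.035 to 0.075 in cohort 1.

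**What a bootstrap correction achieves.** With a Youden cut-off, it reduces the mean bias in sensitivity from 6.4 to 2.2 points (22 events) and from 8.7 to 3.1 points (16 events), with Monte Carlo error of about 0.5.

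**Sampling error for comparison.** Exact 95% intervals are 41% to 83% for 14/22 and 35% to 85% for 10/16.

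**The case against.** A reader might infer that the sensitivity of a debridement-guiding threshold is bound to be overstated by a fixed 7 to 9 points, that the AUC is biased too even if only I_max-post is used, and that a useless marker would appear to discriminate. The documents do not support that much:

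- The size depends on a rule the plan does not name, and nearly vanishes if the cut-off is fixed by specificity.
- The AUC of a single pre-named variable is unbiased, and a useless marker has a mean AUC of 0.50. It does show an apparent Youden index of about 0.15 instead of 0, but the plan never mentions that index and also tests each association.
- The threshold sentence speaks of recurrent infection, which fits cohort 2. Section 7.2 names no threshold for cohort 1, so the 16-event figure is conditional.
- Sensitivity and specificity are not named as reported measures, although a ROC curve plots them and a threshold read from it carries both.
- Section 2 does not say that this cut-off will feed the debridement tool, and section 7.1 calls the study a pilot assessment.

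It is also fair to say that the chosen cut-off itself is close to the best available (true Youden index 0.44 against a possible 0.46) and that sampling error exceeds the bias. These points limit the size and reach of the concern. They do not supply the missing validation, and the wide sampling error is a further reason to report intervals.

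**Conclusion.** The concern holds in a conditional form. The plan derives a threshold and selects a variable in the same patients in whom performance is shown, without internal validation or intervals. Under section 7.1's inputs and an assumed Youden rule on I_max-post alone, sensitivity at the chosen cut-off would on average be overstated by about 6 to 7 points in cohort 2, and by about 9 points in cohort 1 if a threshold is derived there. Specificity is affected by only about 1 to 3 points. The AUC is inflated only through choosing the highest-AUC variable, which section 7.2 does plan.

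The figures assume normally distributed values and that section 7.1's difference and standard deviations apply to I_max-post. The number of candidates and their correlation are assumptions, because the documents give neither. No patient in this study is managed by the cut-off, so the issue is the reliability of the reported result. It should be settled before the analysis is run.

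**What to change.** In the Study Summary and section 7.2:

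1. Name the cut-off criterion in advance, and say in which cohorts a threshold will be derived.
2. Repeat both the variable selection and the threshold derivation in every bootstrap sample.
3. Report optimism-corrected AUC, sensitivity and specificity with 95% intervals, and a bootstrap interval for the cut-off in a.u.
4. State that, in simulation with a Youden cut-off, the correction still leaves about 2 to 3 points of optimism in sensitivity.
5. Label the cut-off exploratory and in need of confirmation in new patients.

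The cost is some wording and a short addition to the analysis code. No extra patients or data are needed. The reported performance will look less favourable.

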1.1 Background Information

The focus of this Phase 1 clinical study is to (1) establish the range and variation associated with bone/soft tissue perfusion in fracture patients, using ICG fluorescence imaging; (2) examine the relationship between perfusion and complications such as surgical site infection (SSI), persistent SSI, and fracture nonunion; (3) to determine whether the quantitative ICG fluorescence can be used to guide bony debridement in the setting of open fracture or infected fracture to minimize complications. This research has been funded by the SYNERGY Pilot Translational Research Grant and by the Department of Orthopaedics.

Infection following trauma is one of the most prevalent and challenging complications faced by orthopedic surgeons in both military and civilian populations, occurring after up to 60% of open bone fractures¹⁻⁷. Several factors specific to this trauma place patients at high risk for infectious complications, including: traumatized tissues, open contaminated fracture, soft tissue coverage issues, catabolic state due to polytrauma, prolonged hospitalization with exposure to nosocomial bacteria, and presence of metallic implants⁸. Infection requires one or more unplanned surgical procedures and leads to prolonged morbidity, loss of function, and potential loss of limb^{1, 9-11}. Failed treatment for bone infection results in recurrent infection, requiring repeat surgical procedures in approximately 30% of patients.¹²⁻¹⁵

Deficient perfusion prevents delivery of antibiotics and endogenous immune cells to traumatized tissues. In the setting of open fracture and established infection, poorly perfused bone is a nidus for biofilm formation creating resistance to antibiotics. Because of this, initial management of open fractures and the management of SSIs at the fracture site are based on aggressive, thorough debridement in an effort to remove all poorly perfused bone. However, there is a critical lack of data to objectively inform bone perfusion and the corresponding amount of tissue to debride. This extensive gap in our understanding leads to substantial variation in extent of debridement and places patients at unnecessarily high risk for initial SSI and recurrent SSI.

While, to date, there is no gold standard technique established to measure bone perfusion in human patients, dynamic contrast-enhanced MRI (DCE-MRI) is the imaging modality that has been used most frequently and effectively to measure bone perfusion in patients without metal implants implants¹⁶⁻²¹. Because of this, developing a better understanding of the relationship between DCE-MRI, which assesses the bone and surrounding soft tissues in a three-dimensional format and ICG-based DCE-FI, which is surface-weighted, is an important next step. Data acquired from intraoperative DCE-MRI and DCE-FI will be used to create a fluorescence-imaging specific model which will correct for the surface-weighted nature of fluorescence imaging and more accurately reflect the fluorescence intensity and kinetics throughout the entire depth of the bone.

There are currently no accepted intraoperative tools that can be used to make objective decisions about bone perfusion. Methods currently used to guide debridement are quite rudimentary. Clinical judgement is based on the gross appearance of soft tissue and bone, including color, turgor, and extent of soft tissue stripping. A burr may be used to look for bleeding bone. More extensive debridement is thought to minimize risk of index infection or reduce the rate of persistent infection; however, this comes at the cost of increasingly complex reconstructive procedures to fill bony defects^{22 23, 24}. Clearly what is needed is a functional imaging system which can assess vascular perfusion of surgical field tissue to guide surgeons in the amount of tissue to debride. In turn, this will lead to fewer infections and a more effective treatment of SSIs at the fracture site. Both scenarios will allow patients to return to duty or work sooner.

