Methodology	
This will be a prospective observational trial to better understand the range and variation associated with bone/soft tissue perfusion in fracture patients and examine the relationship between perfusion, measured using quantitative Indocyanine green (ICG) fluorescence and complications such as surgical site infection (SSI), persistent SSI, and fracture nonunion. Primary outcome measure is complication (either infection, recurrent infection or nonunion).
 
Eligible consenting patients will receive standard of care treatment for their fracture or infection including irrigation and debridement of their operative site and/or fracture fixation. Participation in this study has no specific benefit to the subject. This treatment is not expected to alleviate the need for surgical intervention. After exposure, 0.1 mg/Kg ICG will be injected intravenously and video rate ICG fluorescence images will be acquired 20 seconds before and 4 minutes after the injection, each before and after debridement. A subset of 38 post-fracture complication patients will undergo surgical treatment for their infection in Center of Innovation Surgery (CIS) and have either an intraoperative DCE-MRI after exposure but before the ICG injection or a preoperative DCE-MRI. Patients receiving surgery in the CIS will be required to sign an additional CIS-specific consent document, Informed consent with MRI.
 
The need for repeat surgical procedure will be left up to the treating surgeon. If repeat procedure is needed, pre- and post-debridement quantitative ICG fluorescence images will be obtained at each procedure.
 
Study participants will be followed at 2 weeks, 6 weeks, 3 months and 6 months from their index study surgery. Complication including index infection, recurrent infection or delaying union/nonunion will be identified at the time of diagnosis and/or during each participant's assessment that occurs during routine outpatient clinic visit. Detailed information on the infection including date of diagnosis, participant signs and symptoms, culture test results, method of treatment(s), and date of resolution will be documented.

Study Duration	Five years
Study Center(s)	Single-center, Dartmouth-Hitchcock Medical Center

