A Pulse dye densometer (Pulsion Medical Systems), similar to a pulse oximetry probe, will be placed on the patient's finger to acquire an arterial blood input function during ICG injection. After exposure but prior to debridement, 0.1 mg/kg ICG will be injected intravenously. Video rate ICG fluorescence images will be acquired 20 seconds before and 4 minutes after ICG injection. Debridement will then proceed per standard of care. The wound will be irrigated with a minimum of 3 liters irrigation with normal saline. After irrigation and debridement is completed, 0.1 mg/kg ICG will be injected intravenously again and video rate ICG fluorescence images will be acquired 20 seconds before and 4 minutes after ICG injection. There will be a minimum of 5 minutes between ICG infusions to allow ICG to wash out of tissues.

A subset of 30 eligible consenting patients with post-fracture complications will undergo surgical treatment for their infection in CIS at DHMC. Patients receiving surgery in the CIS will be required to sign an additional CIS-specific consent document. For the patients who didn't receive contrast MRI in 48 hours prior to the

operation, after exposure and removal of hardware but prior to pre-debridement ICG injection, four MRI fiducials will be placed on the four corners of the damaged bone area and the MRI sequences will be acquired. Sequences will include a localizer, coronal T1 fast spin echo (FSE), axial short-tau inversion recovery (STIR), a T1 mapping sequence consisting of a T1-weighted 3D FLASH sequence with at least 3 different flip angles, and DCE acquisition, consisting of 3D FLASH sequences before and after the intravenous administration of 0.2 mL/kg Gadoterate meglumine (Dotarem®). The T1 mapping and DCE sequences will be acquired in the same plane (either the coronal or axial) for all patients. The protocol for the DCE acquisition has already been optimized for current clinical applications in the imaging of both bone and soft tissue tumors. For the patients who received MRI within 48 hours prior to the operation, we may use their pre-operation MRI, instead of intra-operative MRI.

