7.2 Data and Statistical Analysis

Patient cohort 1:

For the primary outcome, SSI is the dependent variable and bone and tissue perfusion, as measured by ICG fluorescence, is the independent variable. Unplanned fracture-related reoperation is the secondary dependent variable and bone and tissue perfusion as measured by ICG fluorescence, is the independent variable. Descriptive statistics, including means and standard deviations, will be presented with 95% confidence intervals. To select the most important ICG fluorescence kinetic curve-related variables, we will perform a bivariate analysis evaluating whether each variable predicts infection and we will select the variable with the highest individual area under the receiver operating curve (AUC ROC).

Our primary null hypothesis is that the post-debridement maximum ICG intensity ($I_{max-post}$) among patients with SSI is equal to or greater than that in the non-SSI patient group. The primary alternative hypothesis is that $I_{max-post}$ in the SSI group is smaller than that in the non-SSI group. We will then perform Students t-tests and chi-square analyses (depending on continuous or categorical variable status) to determine unadjusted associations between the most important ICG fluorescence variable and SSI. A p-value of 0.05 or less will be considered significant for differences between SSI and non-SSI groups. We will then apply multiple logistic model including ICG fluorescence and previously identified predictors for SSI³⁷⁻³⁹. Wald test will be used to determine if ICG fluorescence or any other predictors are significant in the model. We set the type I error at 5%. Table 7.1 shows a summary of the study outcomes, corresponding

hypotheses, and method of analysis to be performed. We anticipate that we will demonstrate a statistically significant difference between the maximum post-debridement ICG fluorescence in patients with and without SSI

Table 7.1 Summary of Outcome Analysis Plan for patient cohort 1

Objective	Outcome		Hypothesis	Method of analysis
	Name	Type		
Determine the association between post-debridement bone perfusion as measured by quantitative ICG fluorescence and surgical site infection (SSI) in patients with open fracture	SSI	Binary	Mean perfusion will be lower among patients who develop SSI	Students t-test Multivariable logistic regression

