	Unplanned fracture-related reoperation	Binary	Mean perfusion will be lower among patients who require unplanned fracture-related reoperation	Students t-test Multivariable logistic regression

Patient cohort 2:

For the primary outcome, treatment failure will be the dependent variable and bone and tissue perfusion, as measured by ICG fluorescence will be the independent variable. Descriptive statistics, including means and standard deviations, will be presented with 95% confidence intervals. To select the most important ICG fluorescence kinetic curve-related variables, we will perform a bivariate analysis evaluating whether each variable predicts infection and we will select the variable with the highest area under the curve (AUC).

Our primary null hypothesis is that the post-debridement maximum ICG intensity ($I_{max-post}$) among patients with persistent SSI/treatment failure is equal to or greater than that in the non-persistent SSI/non-treatment failure patient group. The primary alternative hypothesis is that $I_{max-post}$ in the persistent SSI/treatment failure

group is smaller than that in the non-persistent SSI/non-treatment failure group. We will then perform a Students t-test to determine the association between the most important ICG fluorescence variable and persistent SSI/treatment failure. A p-value of 0.05 or less will be considered significant for differences between persistent SSI/treatment failure and non-persistent SSI/non-treatment failure groups.

We will then apply multiple logistic model including ICG fluorescence and previously identified predictors for persistent SSI/treatment failure³⁷⁻³⁹. Wald test will be used to determine if ICG fluorescence or any other predictors are significant in the model. We set the type I error at 5%. Table 7.2 shows a summary of the study outcome, corresponding hypotheses and method of analysis to be performed. We anticipate that we will demonstrate a statistically significant difference between the maximum post-debridement ICG fluorescence in patients who fail treatment for their SSI resulting in persistent SSI/treatment failure and those who do not.

For subset cohort 2-1, for each DCE-MR and DCE-FI parameter, statistics of median and percentiles will be calculated for each of ROIs. Due to the small cohort size, the correlations between DCE-MRI and DCE-FI will be utilized to analyze the data of each corresponding ROI, assuming that all ROIs in each subject were independent⁴⁰.

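### Section 1.1 promises a model that corrects fluorescence for bone depth, but the cohort 2-1 analysis stops at a correlation with ROIs treated as independent

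*Combined protocol and SAP*

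**What the plan says.** Section 1.1 describes fluorescence as surface-weighted and DCE-MRI as three-dimensional. It says the paired data "will be used to create a fluorescence-imaging specific model which will correct for the surface-weighted nature of fluorescence imaging". The goal given for the corrected result is that it should "more accurately reflect the fluorescence intensity and kinetics throughout the entire depth of the bone". The sentence before it gives a softer aim, a better understanding of how the two measurements relate.

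Section 7.1 says the strength of the relationship in cohort 2-1 will "be assessed by determining the zero-order correlation and resulting R2 metric". It sizes the subset at 21 for an expected r of 0.85 (95% CI 0.55 to 1.00), adds seven patients to optimise the MRI settings, and arrives at 30.

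Section 7.2 says that, for every parameter of either method, "statistics of median and percentiles will be calculated for each of ROIs". As for the analysis itself, it says that "the correlations between DCE-MRI and DCE-FI will be utilized to analyze the data of each corresponding ROI". The same sentence assumes that all ROIs within a subject are independent and gives the small cohort size as the reason.

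On timing, Section 6 (Surgical Procedures) places the intraoperative MRI "after exposure and removal of hardware but prior to pre-debridement ICG injection", or allows a preoperative scan from the preceding 48 hours. The Study Summary agrees: patients "have either an intraoperative DCE-MRI after exposure but before the ICG injection or a preoperative DCE-MRI".

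**The concern.** A correction model needs three things: an equation that turns a fluorescence reading into an estimate of full-depth perfusion, a statement of how wrong that estimate is likely to be in a new patient, and some evidence that the relationship concerns depth and not only the surface. The cohort 2-1 plan supplies none of them. No model form, depth-specific MRI variable, fitting method or validation step is given anywhere in the document. The secondary objective in Section 2, to develop hardware and software tools, has no analysis attached either.

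The independence assumption is a second weakness in the same paragraph. ROIs in one patient share the same limb, circulation, injection and scan. Counting each as a separate observation can make the correlation look better determined than it is.

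At stake is what the subset can support at the end: a measure of association with possibly optimistic precision, where Section 1.1 leads the reader to expect a usable correction.

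**Working it through.** **The plan's own figure.** Inputs from Section 7.1: r = 0.85, interval 0.55 to 1.00 (width 0.45), type I error 0.05, type II error 0.20, n = 21.

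- Precision formula for a correlation, n = 4(1 − r²)²(z/w)² + 3. With w = 0.45: 4 × 0.2775² × (1.96/0.45)² + 3 = 8.8, so 9. The second-stage adjustment gives 12. With w = 0.30 the two stages give 17 and 19.
- Fisher-z test of 0.85 against 0.55 at 80% power, n = (zα + zβ)²/(1.2562 − 0.6184)² + 3. Two-sided: 22.3, so 23. One-sided: 18.2, so 19.

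None of these gives exactly 21. Several come within two patients, but the precision formula at the stated width does not. The point does not depend on this: on any route, 21 is a number for one correlation, not for building or validating a model. (Separately, 21 + 7 = 28, not 30, and the Study Summary gives 38 for the subset. Those figures need reconciling in their own right.)

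**What a correlation delivers.** A straight-line calibration of MRI on fluorescence has slope b = r × SD(MRI)/SD(FI) and intercept mean(MRI) − b × mean(FI). For any constants a and c > 0, corr(a + c·FI, MRI) = corr(FI, MRI), so r alone fixes neither slope nor intercept. For this subset the listed summaries are medians and percentiles, so the line cannot be recovered exactly from them.

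**What R2 delivers.** At r = 0.85, R2 = 0.7225 and the residual SD is √(1 − 0.7225) = 0.53 of the MRI parameter's SD. In-sample scatter about a line can therefore be read from R2. Error in a patient not used for fitting cannot.

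**Promise and plan side by side.**

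| Needed for the Section 1.1 model | Planned for cohort 2-1 |
|---|---|
| Calibration equation | Not specified |
| Out-of-sample prediction error | Not specified |
| Surface versus full-depth comparison | ROI depth not defined |
| Allowance for several ROIs per patient | ROIs assumed independent |
| Strength of relationship | r and R2 |

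**Clustering.** The number of ROIs per patient is not given. Assume m = 1, 2 or 4 ROIs in each of 21 patients, r = 0.85, and interval tanh(1.2562 ± 1.96/√(N − 3)):

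| ROIs per patient (assumed) | N if ROIs are independent | 95% interval | Width |
|---|---|---|---|
| 1 | 21 | 0.66 to 0.94 | 0.28 |
| 2 | 42 | 0.74 to 0.92 | 0.18 |
| 4 | 84 | 0.78 to 0.90 | 0.12 |

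If ROIs in a patient carry little separate information, the first row is close to the truth however many ROIs are drawn. If they really are independent, the lower rows are right. The plan assumes the second case without giving evidence for it.

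**The case against.** The strongest reply is that the model sentence sits in the background section. Neither the objectives nor the endpoints list a depth-correction model. Section 7.1 states its aim as the strength of the relationship, and a correlation answers that. This stands, and it is why the point is minor.

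Four stronger readings are tempting, and the documents do not support them.

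- *That MRI before debridement is itself a defect.* The intraoperative scan comes just before the pre-debridement ICG injection, so it pairs naturally with that series. Section 7.2 does not name the series to be used, but it speaks of corresponding ROIs. One clarifying phrase is enough.
- *That the subset fails to support a correction of the primary predictor.* The cohort 1 and 2 hypotheses ("Our primary null hypothesis is that the post-debridement maximum ICG intensity") use the measured value. Nowhere does the plan say it will be depth-corrected.
- *That a high r could hide fluorescence reading some fraction of the MRI value.* Fluorescence is in arbitrary units and nothing puts MRI on the same scale, so bias in that sense has no meaning here.
- *That the ROI summaries discard depth information.* The sequences are three-dimensional, several percentiles are planned, and ROI depth is undefined. The loss is possible but not stated.

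It is also fair to say that calibration-slope imprecision calculated from r and n would not show harm: it would assume one observation per patient, which is not the plan.

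**Conclusion.** The concern holds in a limited form. Section 1.1 announces a correction model, and the cohort 2-1 analysis neither specifies nor tests one. Followed as written, it yields per-ROI summaries, r and R2, with no calibration equation and no out-of-sample prediction error. The independence assumption can overstate precision. In the illustration, counting four ROIs per patient as independent cuts the interval width from 0.28 to 0.12. That rests on an assumed ROI count and on the extreme case in which ROIs within a patient are fully redundant, so the true effect could be anywhere from nil to that size.

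Severity is minor. No primary test, endpoint or sample size for cohorts 1 to 3 is affected, and the planned correlation is adequate for the narrower aim in Section 7.1.

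**What to change.** In Section 7.2, cohort 2-1:

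1. Fit a linear mixed model with the full-depth DCE-MRI parameter as outcome, the pre-debridement DCE-FI parameter as predictor and patient as random effect.
2. Report slope, intercept and leave-one-patient-out prediction error, predicting each left-out patient from the fixed effects only. Keep r and R2 as descriptive.
3. Where MRI resolution allows, repeat the model with the superficial-layer MRI parameter as outcome and compare the two. This shows whether fluorescence tracks surface or full-depth perfusion. The documents do not give MRI resolution or ROI depth, so this step is conditional.

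This calibrates fluorescence to an MRI measure of full-depth perfusion. It is not in itself a reconstruction of fluorescence through the bone, and the text should say so. If the sponsor does not intend to build the correction model in this study, restate the Section 1.1 sentence as future work.

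The cost is protocol and SAP wording, some extra image analysis and a more modest claim for the subset. No additional patients or scans are needed.
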